5.2.2.4. Reverse Cumulative Distribution Curves

Empirical RCDCs will plot proportions of participants with values equal to or exceeding a specified assay value versus the indicated assay value, for all observed assay values. Data points will be joined by a step function with the line first going down and then to the right to the next assay value.

5.2.2.5. Analysis of Covariance

The ANCOVA model will use logarithmically transformed assay results 1 month after vaccination as dependent variables by controlling baseline assay results (in logarithm scale) to compare the immune response in the experimental group(s) with the reference group (individual vaccine alone). LS GMTs and LS GMRs will be calculated from the model-adjusted group means, group mean differences, and corresponding CIs on the natural log scale by exponentiating the results.

5.3. Methods to Manage Missing Data

5.3.1. Safety Data

Standard algorithms for handling missing AE dates and missing AE severity levels will be applied as described in the safety rulebook summary.

Missing data handling rules on the safety data are described in detail in the corresponding endpoint sections.

5.3.1.1. Reactogenicity Data

For derived variables based on the reactogenicity data, if any day of the 7-day e-diary is available, the “any day (Days 1-7)” data will be considered nonmissing.

The reactogenicity data are mostly collected through the e-diary, which does not allow participants to skip the question. Therefore, for a specific day, if the e-diary data are transferred for that day, all of the reactogenicity data for the participant on that day are nonmissing.

In general, for any participant with all 7 days of the e-diary data missing, this participant will not be included in the analysis (ie, assuming MCAR). If only 1 to 6 days of e-diary data are transferred, it is expected that these reactogenicity events would be queried by the investigator for the missing e-diary days and entered in the AE CRF if any reactogenicity was not reported in the e-diary due to missed days. Therefore, the primary analysis will use reactogenicity recorded in the AE CRF to impute the partially missed e-diary data to estimate the reactogenicity rate during the e-diary collection period. The AE CRF is designed as a log page, which means only events that occurred will be recorded and events that did not occur will not be recorded. Therefore, all remaining missing days are considered as “no.” This imputation can reasonably estimate the reactogenicity event rates during the e-diary collection period. However, data for the missing day(s) will not be imputed in the analysis of each specific day.

A sensitivity analysis will be planned for participants who completed the e-diary. Only participants with all 7 days of e-diary transferred data will be included in this sensitivity analysis.

5.3.2. Immunogenicity Data

Any assay results above LLOQ are considered accurate, and their quantitated values will be reported. Values below the LLOQ, denoted as BLQ, will be set to $0.5 \times \text{LLOQ}$ for analysis.

For calculating a fold rise, $< \text{LLOQ}$ will be converted to $0.5 \times \text{LLOQ}$ for a numerator, and $< \text{LLOQ}$ will be converted to LLOQ for a denominator when only 1 of either the numerator or denominator is $< \text{LLOQ}$. If both the numerator and denominator are $< \text{LLOQ}$, then both will be converted in the same way.

The LLOQs for each assay will be included in the final released assay data.

Values for sera that are designated as QNS, indeterminate results, or values recorded as “not done” will be set to “missing.” Additionally, any time point with no blood draws will not be included in the analysis. No imputation will be done for these missing values, as MCAR is assumed for immunogenicity data according to Scott and Hsu.⁴

6. ANALYSES AND SUMMARIES

6.1. Primary Endpoints

6.1.1. Primary Immunogenicity Endpoints for Combined Vaccine Coadministered With QIV (Group 1) Noninferiority Objective

6.1.1.1. Main Analysis

- Estimand strategy: Hypothetical approach ([Section 2.2.1.1](#)).
- Analysis set: Evaluable immunogenicity population ([Section 4](#)).
- Analysis timing: Final analysis of immunogenicity objective.
- Intercurrent events and missing data: All data collected after or at intercurrent events will not be included ([Section 2.2.1.1](#)); missing data will not be imputed ([Section 5.3.2](#)).
- Analysis methodology: GMR, defined as the ratio of all of the 8 strain/subgroup-specific serology results measured by RSV NT, SARS-CoV-2 NT, and HAI GMTs in Group 1 to that for single vaccine administered alone (eg, Groups 3, 4, and 5) at Visit A102 will be summarized along with the 97.5% CI ([Section 5.2.2.3](#)). Descriptive statistics, including sample size (n), and GMTs at Visit A102 will be presented for Group 1 as well as Groups 3, 4, and 5 ([Section 5.2.2](#)).
- RCDCs for each of the 8 strain/subgroup-specific serology results at Visit A102 measured by RSV NT, SARS-CoV-2 NT, and HAI titers will be plotted after vaccination for the applicable groups (eg, HAI titers for Group 1 vs Group 5).

6.1.1.2. Supplementary Analysis

To support the assessment of immunogenicity, supplementary analysis will be performed based on the mITT immunogenicity population using the same presentation as specified in the main analysis, except that RCDC will not be presented.

6.1.2. Primary Immunogenicity Endpoints for Combined Vaccine (Group 2) Noninferiority Objective

6.1.2.1. Main Analysis

- Estimand strategy: Hypothetical approach ([Section 2.2.1.1](#)).
- Analysis set: Evaluable immunogenicity population ([Section 4](#)).
- Analysis timing: Final analysis of immunogenicity objective.
- Intercurrent events and missing data: All data collected after or at intercurrent events will not be included ([Section 2.2.1.1](#)); missing data will not be imputed ([Section 5.3.2](#)).
- Analysis methodology: GMR, defined as the ratio of all of the 4 strain/subgroup-specific serology results measured by RSV NT and SARS-CoV-2 NT GMTs in Group 2 to that in single vaccine administered alone (eg, Groups 3 and 4) at Visit A102 will be summarized along with the 97.5% CI ([Section 5.2.2.3](#)). Descriptive statistics, including sample size (n), and GMTs at Visit A102 will be presented for Group 2 and Groups 3 and 4 ([Section 5.2.2](#)).
- RCDCs for each of the 4 strain/subgroup-specific serology results at Visit A102 measured by RSV NT and SARS-CoV-2 NT will be plotted after vaccination for the applicable groups (eg, RSV A NT for Group 2 vs Group 4).

6.1.2.2. Supplementary Analysis

To support the assessment of immunogenicity, supplementary analysis will be performed based on the mITT immunogenicity population using the same presentation as specified in the main analysis, except that RCDC will not be presented.

6.1.3. Local Reactions and Systemic Events

Analyses of reactogenicity endpoints are based on the safety population that includes participants with any e-diary data reported after vaccination. Reactogenicity data ([Section 3.1.2.1](#) and [Section 3.1.2.2](#)) will be summarized by vaccine group, according to the study interventions the participants actually received.

6.1.3.1. Main Analysis

- Estimand strategy: Treatment policy ([Section 2.2.1.3.1](#)).
- Analysis set: Reactogenicity safety population (only participants with at least 1-day e-diary data transferred are included in the calculation) ([Section 5.3.1.1](#)).
- Analysis methodology: 95% CI of the proportion of participants reporting each event will be calculated using the Clopper-Pearson method ([Section 5.2.1](#)).
- Analysis timing: Final analysis of immunogenicity objective.
- Intercurrent events and missing data: All data collected are included; partially missing e-diary data are imputed as “no” ([Section 5.3.1.1](#)); e-diary data that are confirmed as errors will not be used for analysis.
- Descriptive statistics, including the proportion (%), the numerator (n) and the denominator (N) used in the proportion calculation, and the 95% CI for percentage using the Clopper-Pearson method, will be presented for each group ([Section 5.2.1](#)).
- Bar charts with the proportions of participants for each and any local reaction and each and any systemic event throughout the 7 days will be plotted for each vaccine group. The bars will be divided into severity categories to highlight the proportions of participants by maximum severity.

6.1.3.2. Supplementary Analysis

To support the assessment of reactogenicity, the endpoints below, as specified in [Section 3.1.2.1](#) and [Section 3.1.2.2](#), will be summarized per the supplementary analysis with the same analysis population:

- Duration (days) of each local reaction and each systemic event after vaccination.
- Onset day of each local reaction and each systemic event after vaccination.

The presentation of the results will include a basic descriptive summary without the 95% CIs for each vaccine group.

6.1.3.3. Sensitivity Analysis

Two sensitivity analyses will be conducted:

- Maximum severity of reactogenicity is assessed on participants with all 7 days of e-diary data transmitted.
- Maximum severity of reactogenicity is also assessed using the e-diary data only. The difference between the primary analysis and this analysis will also be presented.

6.1.4. AEs and SAEs

AEs and SAEs will be summarized by vaccine group, according to the study interventions the participants actually received. All AEs after informed consent and prior to the first vaccination will not be included in the analyses but will be listed.

6.1.4.1. Main Analysis

- Estimand strategy: Treatment policy ([Section 2.2.1.3.1](#), [Section 2.2.1.3.2](#), and [Section 2.2.1.3.3](#)).
- Analysis set: Safety population ([Section 4](#)).
- Analysis timing: Final analysis of immunogenicity objective; final database release.
- Intercurrent events and missing data: All data collected are included.
- Analysis methodology: 95% CIs of the proportion of participants reporting those events will use the Clopper-Pearson method ([Section 5.2.1](#)).
- Descriptive statistics, including the proportion (%), the numerator (n) and the denominator (N) used in the proportion calculation, and the 95% CI for percentage using the Clopper-Pearson method, will be presented for each vaccine group ([Section 5.2.1](#)).
- Bar charts with the proportions of participants for each variable will be plotted for each group. The bars may be divided into relatedness categories to highlight the proportions of participants with related events.
- The main analysis would be based on AEs excluding the reactogenicity events that were reported in the AE CRF (except for SAEs) ([Section 3.1.2.3](#)).

6.1.4.2. Supplementary Analysis

To support the assessment of AEs, the endpoints below, as specified in [Section 3.1.2.3](#), will be summarized with the same analysis population using the same presentation as specified in the main analysis:

- Immediate AEs after vaccination
- Related AEs reported through 1 month after vaccination
- Severe or life-threatening AEs reported through 1 month after vaccination
- AEs leading to withdrawal
- AEs leading to death
- AESIs

6.1.4.3. Sensitivity Analysis

In addition, a sensitivity analysis will be conducted by using all AEs (including reactogenicity reported in the AE CRF during the e-diary collection period).

6.2. Secondary Endpoints

Analyses will be similar to the primary endpoint, except that Group 1 will be replaced with Group 7 and Group 2 will be replaced with Group 6.

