10.11.6. Substudy A Design

10.11.6.1. Overall Design

This is a Phase 1/2 randomized, parallel-group, observer-blinded substudy to describe the safety, tolerability, and immunogenicity of a combined RSVpreF and bivalent BNT162b2 (original/Omi BA.4/BA.5) vaccine [RSVpreF+BNT162b2], administered concomitantly with a seasonal influenza vaccine or administered alone. Approximately 1050 healthy participants ≥ 65 years of age will be enrolled in Substudy A.

Note: "Enrolled" means a participant's, or their legally authorized representative's, agreement to participate in a clinical study following completion of the informed consent process.

Randomization will be conducted across 2 enrollment strata (see Table 4).

Table 4. Substudy A Enrollment Strata

Enrollment Stratum	Total Number of Participants	Number of Participants per Vaccine Group	Vaccine Group Number	Vaccine Group Description
1	750	150	1	[RSVpreF+BNT162b2] administered concurrently in the opposite arm to licensed QIV
		150	2	[RSVpreF+BNT162b2] administered concurrently in the opposite arm to placebo
		150	3	Bivalent BNT162b2 administered concurrently in the opposite arm to placebo
		150	4	RSVpreF administered concurrently in the opposite arm to placebo
		150	5	Licensed QIV administered concurrently in the opposite arm to placebo
2	300	150	6	RSVpreF and bivalent BNT162b2 (2 injections in the same arm) coadministered concurrently in the opposite arm to placebo
		150	7	RSVpreF and bivalent BNT162b2 (2 injections in the same arm) coadministered concurrently in the opposite arm to QIV

All participants will be asked to complete a reactogenicity e-diary for 7 days following vaccination. Blood samples of approximately 50 mL will be collected for immunogenicity assessments prior to vaccination at Visit A101 and 1 month after vaccination (Visit A102).

E-diary data from Day 1 through Day 3 for the first 50 participants in Groups 1 to 5, and the first 20 participants in Groups 6 and 7, will be evaluated prior to enrollment of the remaining participants in each group.

AEs and SAEs will be collected from the signing of informed consent through Visit A102 (1-month follow-up visit). SAEs will be collected from the signing of informed consent through Visit A103 (6-month telephone contact).

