10.11.8.1.4. Allocation to Study Intervention

See [Section 6.3](#).

Allocation of study intervention at Visit A101 in Substudy A will be conducted via the IRT.

E-diary data from Day 1 through Day 3 for the first 50 participants in Groups 1 to 5, and the first 20 participants in Groups 6 and 7, will be evaluated prior to enrollment of the remaining participants in each group. Initial enrollment will be controlled through the IRT system to manage this approach.

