10.11.11.3.3. Secondary Endpoint(s)/Estimand(s) Analysis

Endpoint	Statistical Analysis Methods
Secondary immunogenicity	
 • GMRs of RSV A and RSV B NTs (Group 7 to Group 4), GMRs of SARS-CoV-2 Omicron BA.4/BA.5–strain NTs and reference-strain NTs (Group 7 to Group 3), influenza strain-specific GMRs of HAI titers (Group 7 to Group 5) at 1 month after vaccination will be provided with 97.5% CIs (Section 9.3.1.2.3). Using a 2-fold noninferiority margin, success for the first of the secondary immunogenicity objectives will be declared if the lower bound of the 2-sided 97.5% CI for the GMR is greater than 0.5 for both RSV A and RSV B antigens, for both the Omicron BA.4/BA.5 and reference strains, and for all 4 QIV strains, after the first primary immunogenicity objective is achieved. • GMRs of RSV A and RSV B NTs (Group 6 to Group 4) and GMRs of SARS-CoV-2 Omicron BA.4/BA.5–strain NTs and reference-strain NTs (Group 6 to Group 3) at 1 month after vaccination will be provided with 97.5% CIs (Section 9.3.1.2.3). Using a 2-fold noninferiority margin, success for the second of the secondary immunogenicity objectives will be declared if the lower bound of the 2-sided 97.5% CI for the GMR is greater than 0.5 for both RSV A and RSV B antigens and for both the Omicron BA.4/BA.5 and reference strains, after the second primary immunogenicity objective is achieved.

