2.2.2. Secondary Estimands

2.2.2.1. Secondary Immunogenicity Estimands for 3-Vaccine Coadministration Noninferiority Objective

The estimand attributes are the same as the first primary immunogenicity estimand ([Section 2.2.1.1](#)), except:

- **Treatment condition**: Randomized to Group 7, 3, 4, or 5.
- **Intercurrent events**: Participants who were randomized to Group 7 should have received all 3 individual vaccines: RSVpreF, BNT162b2, and QIV.
- **Population-level summary**: GMR, defined as the ratio of each applicable variable GMT, between Group 7 and Groups 3, 4, and 5, respectively.

2.2.2.2. Secondary Immunogenicity Estimands for RSVpreF and BNT162b2 Coadministration Noninferiority Objective

The estimand attributes are the same as the second primary immunogenicity estimand ([Section 2.2.1.2](#)), except:

- **Treatment condition**: Randomized to Groups 6, 3, and 4.
- **Intercurrent events**: Participants who were randomized to Group 6 should have received both individual vaccines: RSVpreF and BNT162b2.
Participants who were randomized to Group 6 should have received 2 individual vaccines: RSVpreF and BNT162b2.
- **Population-level summary**: GMR, defined as the ratio of each applicable variable GMT, between Group 6 and Groups 3 and 4, respectively.

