2.3. Study Design

This is a Phase 1/2 randomized, parallel-group, observer-blinded substudy to assess the safety, tolerability, and immunogenicity of a combined RSVpreF and bivalent BNT162b2 (original/Omi BA.4/BA.5) vaccine, [RSVpreF+BNT162b2], administered concomitantly with a seasonal influenza vaccine or administered alone. Approximately 1050 healthy participants ≥ 65 years of age will be enrolled and randomized to 7 groups across 2 strata, as illustrated below.

All participants will be asked to complete a reactogenicity e-diary for 7 days following vaccination. AEs and SAEs will be collected from the signing of informed consent through Visit A102 (1-month follow-up visit). SAEs will be collected from the signing of informed consent through Visit A103 (6-month telephone contact).

Blood samples will be collected for immunogenicity assessments prior to vaccination at Visit A101 and 1 month after vaccination (Visit A102). Immunogenicity measured by HAI titers for the matched seasonal strains ($2\times A$, $2\times B$) recommended by WHO will be assessed for Groups 1, 5, and 7; immunogenicity measured by SARS-CoV-2 neutralization assay (both reference strain and Omicron BA.4/BA.5) will be assessed for Groups 1, 2, 3, 6, and 7; and immunogenicity measured by RSV A and RSV B serum NTs will be assessed for Groups 1, 2, 4, 6, and 7.

	Vaccination			1-Month Follow-Up Visit	6-Month Telephone Contact
Approximate Month (Visit Window)	0 (Day 1)			1 (28 to 35 Days After Vaccination)	6 (175 to 189 Days After Vaccination)
Visit Identifier	Visit A101			Visit A102	Visit A103
	Vaccination 1 (Right Arm)		Vaccination 2 (Left Arm)	Vaccination 3 (Right Arm)	
Group 1 (n=150)	 Combination [RSVpreF+BNT162b2]	QIV			
Group 2 (n=150)	 Combination [RSVpreF+BNT162b2]	Placebo			
Group 3 (n=150)	 Bivalent BNT162b2	Placebo			
Group 4 (n=150)	 RSVpreF	Placebo			
Group 5 (n=150)	 QIV	Placebo			
Group 6 ^a (n=150)	 Bivalent BNT162b2	Placebo	RSVpreF		
Group 7 ^a (n=150)	 Bivalent BNT162b2	QIV	RSVpreF		
 Blood collection  Telephone contact					

a. Separate administration sites on right arm by 1 inch (2.5 cm).

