5.2.2.3. Geometric Mean Ratios

The GMRs will be calculated as the mean of the difference of logarithmically transformed assay results between 2 groups and exponentiating the mean. Two-sided CIs will be obtained by calculating CIs using the Student t distribution for the mean difference of the logarithmically transformed assay results and exponentiating the confidence limits.

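### The secondary noninferiority tests use an unadjusted GMR, although the SAP already plans a baseline-titer ANCOVA for the same groups that could decide them with more power

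*SAP*

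**What the plan says.** - **Tests.** The secondary objectives are formal hypothesis tests (SAP 5.1): 8 for Group 7 against Groups 3, 4 and 5 (5.1.3) and 4 for Group 6 against Groups 3 and 4 (5.1.4). Each set is tested after its matching primary objective is met. Protocol 10.11.11.3.3 gives the rule: "success for the first of the secondary immunogenicity objectives will be declared if the lower bound of the 2-sided 97.5% CI" lies above 0.5 for every antigen. The second secondary objective has the same form.
- **Method.** SAP 6.2 carries over the primary method: "Analyses will be similar to the primary endpoint, except that Group 1 will be replaced with Group 7". That method is SAP 5.2.2.3: "Two-sided CIs will be obtained by calculating CIs using the Student t distribution for the mean difference of the logarithmically transformed assay results". It has no covariate.
- **ANCOVA.** SAP 5.2.2.5 defines a model for the 1-month log titer "by controlling baseline assay results (in logarithm scale) to compare the immune response in the experimental group(s) with the reference group". SAP 6.3.5.2 fits it to Groups 1, 2, 6, 7 and 4 for RSV, Groups 1, 2, 6, 7 and 3 for SARS-CoV-2, and Groups 1, 7 and 5 for HAI. It is listed as a sensitivity analysis with 95% CIs.
- **Strata.** Protocol 10.11.6.1 says "Randomization will be conducted across 2 enrollment strata (see Table 4"). Table 4 there puts Groups 1-5 in stratum 1 and Groups 6-7 in stratum 2. SAP 2.3 says participants "will be enrolled and randomized to 7 groups across 2 strata, as illustrated below", and SAP 2.2.2.1 gives the treatment condition as "Randomized to Group 7, 3, 4, or 5". On the staged start of enrollment, Protocol 10.11.8.1.4 says only "Initial enrollment will be controlled through the IRT system to manage this approach".

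**The concern.** Each secondary objective succeeds only if all of its 8 or 4 tests succeed, so the noisiest antigen largely sets the power. In Protocol Table 5 that is SARS-CoV-2 BA.4/BA.5, with SD 1.5 on the natural-log scale and 93.8% power. Visit A101 blood is drawn from every participant for immunogenicity, and the SAP already specifies a model that uses those titers. Yet that model is reported at a confidence level that cannot settle any secondary hypothesis, while the analysis that ignores baseline makes the decision. What is at stake is the chance of missing a secondary objective that is truly met. The primary objectives are not part of this point.

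All 12 secondary contrasts also run between the two enrollment strata, and neither document says how a participant enters a stratum. That is a gap in the description and is treated separately below.

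**Working it through.** **Inputs from Protocol 10.11.11.5 and Table 5.** n = 135 evaluable per group; true GMR 1; margin ln 2 = 0.693; 1-sided alpha 0.0125. Log-scale SDs are 1.1 (RSV A, RSV B, H1N1, H3N2), 1.2 (each B strain), 1.3 (SARS-CoV-2 reference) and 1.5 (BA.4/BA.5). Overall power is the product over tests, treated as independent.

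**Step 1: reproduce the plan.** SE = SD x sqrt(2/135), noncentrality = 0.693/SE, df = 268, critical t = 2.254.

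| SD | SE | Noncentrality | Power | Table 5 |
|---|---|---|---|---|
| 1.1 | 0.134 | 5.18 | 99.8% | 99.8% |
| 1.2 | 0.146 | 4.75 | 99.3% | 99.3% |
| 1.3 | 0.158 | 4.38 | 98.3% | 98.3% |
| 1.5 | 0.183 | 3.80 | 93.8% | 93.8% |

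The products are 90.3% for 8 tests (stated 90.2%) and 91.9% for 4 tests (stated 91.8%). The differences are rounding.

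**Step 2: ANCOVA with complete baselines.** The residual SD is SD x sqrt(1 - r^2), with one df lost (267). The documents do not give r; 0.3 to 0.5 is assumed. This is a two-group calculation. Fitting the 3 or 5 groups of SAP 6.3.5.2 adds error df and changes it negligibly.

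| | SD factor | BA.4/BA.5 alone | All 8 | All 4 |
|---|---|---|---|---|
| Unadjusted | 1 | 93.8% | 90.3% | 91.9% |
| r = 0.3 | 0.954 | 95.7% | 93.8% | 94.6% |
| r = 0.5 | 0.866 | 98.3% | 97.9% | 98.0% |

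**Step 3: missing baselines.** The evaluable population (SAP 4) requires a 1-month result but no Visit A101 result. If a fraction L lacks a baseline and is dropped, ANCOVA breaks even when (1 - r^2)/(1 - L) is about 1, that is, r is about sqrt(L). Solving with the exact power gives r = 0.14, 0.22 and 0.32 for L = 2%, 5% and 10%.

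| Missing (n per group) | All 8, r = 0.3 | All 8, r = 0.5 |
|---|---|---|
| 2% (132) | 93.1% | 97.6% |
| 5% (128) | 92.0% | 97.1% |
| 10% (122) | 90.0% | 96.2% |

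At r = 0.3 with 10% missing, ANCOVA falls slightly below the unadjusted 90.3%.

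**Step 4: would ANCOVA guard against a stratum difference?** As an illustration only, put the true GMR at the margin for one test with SD 1.5 (nominal error 1.25%). Assume that stratum 2 titers are shifted favorably by 0.2 on the log scale.

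| Analysis | False noninferiority |
|---|---|
| Unadjusted | 12.5% |
| ANCOVA, baseline carries half the shift | 4.7% (r = 0.3) to 5.3% (r = 0.5) |
| ANCOVA, baseline carries none of it | 13.6% (r = 0.3) to 16.3% (r = 0.5) |

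In the last row the bias is unchanged while the SE is smaller, so the error rises.

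**The case against.** **The plan is already adequate.** The unadjusted GMR is a valid test with about 90% and 92% planned power, and the ANCOVA will be reported anyway. This stands: nothing here is an error. The remaining argument is that the more informative of two planned estimators usually ought to make the decision.

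**The precision argument applies to the primary tests too.** It does. Changing only the secondary tests leaves two estimators in one testing hierarchy, which is a real cost.

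**The gain is not guaranteed.** Correct. It depends on r, which the documents do not give, and on how complete the baselines are (Step 3).

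**It may be too late.** Protocol 2.1 describes Substudy A's formulation in the past tense, and the protocol's references carry October 2023 access dates. The documents give no unblinding date, so the recommendation has to be conditional.

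**The stronger reading.** A reader might infer that the cross-stratum comparisons are not randomized and that ANCOVA is needed to rescue them. The documents do not support this. SAP 2.2.2.1 and 2.3 describe randomization to all the compared groups, and Protocol 6.3 allocates vaccine groups through one IRT. The first cohorts reviewed, 50 in Groups 1-5 and 20 in Groups 6-7 if read as totals, stand in the ratio 50/20 = 2.5. That equals 750/300, the ratio of the stratum sizes. This fits concurrent equal allocation, though it does not prove it. If one list is used, no stratum bias arises.

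**Conclusion.** The point holds as a precision improvement. With r assumed at 0.3-0.5, GMR 1, n = 135 per group, the SDs in Table 5, independent tests and complete baselines, deciding the secondary tests by ANCOVA adds 3.5 to 7.6 percentage points of power for the 8-test objective (93.8 - 90.3; 97.9 - 90.3). For the 4-test objective it adds 2.7 to 6.1 points (94.6 - 91.9; 98.0 - 91.9). The gain shrinks as baselines go missing and disappears below r of about 0.14, 0.22 or 0.32 at 2%, 5% or 10% missing.

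The stratum layout is not the reason for the change. How participants enter a stratum is unstated, and that needs a clarification; it is not evidence of bias. Nor does ANCOVA protect against a stratum difference. It removes only the part carried by baseline titer, and if baseline carries none it slightly increases false noninferiority (Step 4). The shifts in that step are assumed; the documents give no sign of one. The primary contrasts all lie within stratum 1 and are unaffected.

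**What to change.** **If the 1-month unblinding has not occurred**, replace the method in SAP 6.2 with text to this effect:

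> Each secondary hypothesis is tested with the ANCOVA of Section 5.2.2.5 (ln Visit A102 titer on vaccine group and ln Visit A101 titer), fitted to the groups listed for that assay in Section 6.3.5.2. Noninferiority is declared if the lower bound of the 2-sided 97.5% CI for the LS GMR exceeds 0.5. The unadjusted GMR with 97.5% CI is the sensitivity analysis.

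Also:
- State how a participant without a valid Visit A101 titer is handled. SAP 5.2.2.5 is silent and SAP 5.3.2 rules out imputation, so the default would be exclusion from the model.
- Align SAP 2.1 (which now reports no change from the protocol), 2.2.2 (population-level summary), 5.1.3-5.1.4 (hypotheses on adjusted means) and Protocol 10.11.11.3.3.

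**If unblinding has already occurred**, keep the unadjusted rule and report the ANCOVA as supportive. Changing the decision rule at that stage would be worse than leaving it.

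**Separately, as a clarification only**, state in Protocol 10.11.8.1.4 whether the IRT uses one concurrent list for all seven groups.

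**Cost.** No extra participants, visits or samples. Both documents need text edits. Protocol 10.11.11 demands an amendment only for major changes to the primary endpoints or their analyses, but aligning 10.11.11.3.3 and 10.11.8.1.4 still means editing the protocol. The secondary estimator would differ from the primary one unless both are changed. If exclusion is the rule chosen, participants without a baseline titer leave the tested secondary set.
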